3.2.5 Biomarker Analysis Set

Biomarker analysis set consists of all subjects receiving at least one dose of investigational product and having available biomarker data.

3.3 ANALYSIS OF STUDY IMPLEMENTATION

3.3.1 Subject Distribution

The number of subjects who have signed the informed consent form, the number of subjects who have failed the screening, and the number of subjects who have used the study drug will be calculated.

The number and percentage of subjects who have ended treatment with the study drugs BLU-554 and CS1001, as well as the number and percentage of subjects who have ended treatment due to various reasons, will be calculated respectively. The number and percentage of subjects who have withdrawn from the study, as well as the number and percentage of subjects who have withdrawn from the study for various reasons will be calculated, and the reasons for ending treatment and withdrawing from the study will be tabulated.

The number and percentage of subjects included in each analysis set will be calculated and tabulated.

3.3.2 Protocol Deviations

Based on the safety analysis set, important protocol deviations will be summarized and tabulated.

3.3.3 Combined Medications

The analysis will be based on the safety analysis set.

According to the time of the use of combined medications and study drugs, combined medications will be classified into past medications and concomitant medications.

Past medication refers to non-study medication that was started and ended before the first dose of study drug.

Concomitant medication refers to a non-study medication that meets one of the following conditions:

- Started at the same time or after the first dose of study drug.
- Started before the first dose of study drug and continued after the first dose of study drug.

Concomitant medications will be coded according to the World Health Organization Drug Dictionary (WHO-DD) WHODrug-Global-B3 Version 202103. Past medications and concomitant medications will be summarized by 2-level Anatomical Therapeutic and Chemical classification system (ATC) and Preferred Term (PT). If a subject experiences multiple occurrences of the same ATC2 and PT, the subject will be counted only once under the ATC2 and PT.

3.4 DEMOGRAPHIC AND BASELINE CHARACTERISTICS

The analysis will be based on the safety analysis set.

3.4.1 Demographics

Demographic data including age, sex, race, height, weight, baseline Eastern Cooperative Oncology Group (ECOG) score, and other demographic data will be described and tabulated.

3.4.2 Medical History

Tumor diagnosis will be statistically described and tabulated.

Medical histories other than tumors will be coded using the Medical Dictionary for Regulatory Activities (MedDRA) Version 24.0 and summarized by System Organ Class (SOC) and Preferred Term (PT) thereunder.

3.4.3 History of Antitumor Therapy

The history of antitumor drug treatment will be coded and summarized according to the WHO-DD WHODrug-Global-B3 202103 Version.

Previous antitumor treatment regimens, including previous systemic treatment regimens, radiotherapy history, and history of tumor-related surgery/operation will be statistically described.

3.5 SAFETY ANALYSIS

3.5.1 Study Drug Exposure

The analysis will be performed based on the safety analysis set.

The number of cycles of CS1001 treatment received by patients will be summarize and statistically described, and the cumulative exposure, time of exposure (weeks), dose intensity [cumulative exposure/time of exposure (weeks)], relative dose intensity (dose intensity/planned dose intensity*100%), and dose adjustment of the study drugs CS1001 and BLU-554 will be summarized respectively.

The planned dose, the actual dose, the action taken before or during the injection, and the reason for the action will be tabulated.

3.5.2 Dose-Limiting Toxicity

The analysis will be performed based on the dose-determining set.

Dose-limiting toxicity categories will be summarized and tabulated.

3.5.3 Adverse Event

The analysis will be performed based on the safety analysis set.

Adverse events will be coded using MedDRA Version 24.0 and graded according to the National Cancer Institute (NCI) Common Terminology Criteria for Adverse Events (CTCAE) v5.0.

The overall occurrences of treatment-emergent adverse events (TEAEs) will be summarized, and the overall incidence of various TEAEs will be calculated.

For all treatment-emergent adverse events, grade 3 and above TEAEs, serious adverse events (SAEs), TEAEs related to the study drug, SAEs related to the study drug, immune-related TEAEs, infusion-related reactions, and TEAEs leading to discontinuation of the study drug, the number and percentage of subjects will be summarized by System Organ Class (SOC) and Preferred Term (PT). In addition, TEAEs will be summarized by System Organ Class, Preferred Term, and NCI-CTCAE severity.

TEAE is defined as (regardless of severity)

- Any adverse event following initiation of treatment
- Adverse event that exists at the time of initiation of treatment but begins to worsen following initiation of treatment
- Adverse event that has occurred and remitted prior to treatment but recurs following initiation of treatment

TEAEs leading to the adoption of actions related to the study drug need to be summarized separately based on being related or not related to the study drug.

The incidences of various treatment-emergent adverse events will be calculated by SOC and PT thereunder. The default order of adverse event incidences is an inverted order of overall incidence, by SOC first and then by PT thereunder. If the overall incidence of two adverse events is the same, the adverse events will be sorted alphabetically. If a subject experiences multiple occurrences of an adverse event with the same SOC and PT, the subject will be counted only once under the SOC and PT. The incidences of treatment-emergent adverse events will be calculated by SOC, PT and severity. If a subject experiences multiple occurrences of an adverse event with the same PT, the subject will be counted only once under the PT and only the most severe occurrence will be counted.

All adverse events, serious adverse events, grade 3 and above adverse events, adverse events related to the study drug, immune-related adverse events, adverse events leading to discontinuation of the study drug, and adverse events leading to death will be tabulated.

3.5.4 Dead

The analysis will be performed based on the safety analysis set.

All death events will be summarized and tabulated.

3.5.5 Laboratory Data

The analysis will be performed based on the safety analysis set.

At each visit, changes from baseline in quantitative laboratory test results will be summarized, and qualitative results will be summarized for specific laboratory tests.

Specific laboratory findings will be graded according to NCI CTCAE v5.0, and then a cross-tabulation of NCI CTCAE grades for the worst post-baseline measurements versus baseline will be generated.

For liver function laboratory data, the following will be summarized: alanine aminotransferase (ALT) or/and aspartate aminotransferase (AST) ≥ 3 *upper limit of normal (ULN), and total bilirubin (TBIL) > 2 *ULN or TBIL > 1.5 *ULN; ALT and/or AST, ALT, AST ≥ 3 *ULN, 5 *ULN, 10 *ULN, 20 *ULN; TBIL > 1.5 *ULN, > 2 *ULN; alkaline phosphatase (ALP) > 1.5 *ULN.

Abnormal clinical laboratory data results will be tabulated.

3.5.6 12-lead ECG

The analysis will be performed based on the safety analysis set.

At each visit, the overall ECG evaluation will be summarized.

All abnormal and clinically significant 12-lead ECG findings will be tabulated.

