- c. Safety visits: For subjects who have completed treatment, a safety visit should be conducted on the 30th day (±7 days), 60 days (±7 days), and 90 days (±7 days) post the last dose; the safety follow-up at 90 day post the last dose can be conducted at the same day as that for the first survival follow-up. Survival follow-up: subjects will be contacted by telephone or in person every 12 weeks from the last dose of study drug to collect survival status, subsequent anti-tumor therapy, and study drug-related SAEs until the death, loss of follow-up, withdrawal from the study, or study termination, whichever occurs first.
- d. Consent for the study may be obtained from the subjects by written.
- e. A complete medical history will be obtaining at the Screening visit. Only disease-related symptoms and changes from the previous visit need to be collected on C1D1.
- f. A complete physical examination will be performed at the Screening visit. Subsequent physical examinations will be disease- and AE-focused.
- g. To be performed for women with childbearing potential within 7 days of C1D1. A serum pregnancy test should be performed at Screening; thereafter, a serum or urine pregnancy test should be performed on every odd cycle (e.g., C3, C5).
- h. To be performed on D1 ( $\pm 4$  days) of every odd cycle starting with C3.
- i. ECGs (12-lead) exams will be performed after at least a 10 minute rest in the supine position. ECGs will be performed at Screening and during treatment, at EOT, and at Safety Follow-Up. In case of PK sampling, ECG should be performed for 3 consecutive times with an interval of 5 minutes each time in Cycle 1, 2 and 4. Refer to Table 4 and Table 5 for specific time. For other treatment cycles ECG should be performed at predose of any Cycle Day 1 dosing. For C1D2,

ECG should be collected at predose. Frequency of ECGs may be increased if clinically indicated.

- j. To be performed as clinically indicated.
- k. Imaging assessment of tumors: Tumor assessment is conducted according to the standard RECIST v1.1. See the specific assessment standards in Appendix 2.

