		BLU-554 dosing			CS1001 dosing b				
		30 min	$\pm 5 \min$	Х					
		1h	$\pm 5 \min$	Х					
	D1	2h c, e	$\pm 10 \min$	Х	EOI+30 min c, e	± 15 min	Х		X
	DI	4h	$\pm$ 15 min	Х					
Cycle 1		6h	± 15 min	Х					
2		7.5h			EOI+6h	± 30 min	Х		
		8h	$\pm$ 30 min	Х					
	D2	24h d	$\pm 1h$	Х	EOI+22.5h d	$\pm 1h$	Х		X
	D8	168h			EOI+168 h	$\pm 1 \text{ day}$	Х		
	D15	336h			EOI+336h	$\pm 1 \text{ day}$	Х		
		0 (Predose)	30 min prior to dosing	X	0 (Predose)	30 min prior to dosing	X	Х	X
		BLU-554 dosing b			CS1001 dosingb				
		30 min	$\pm 5 \min$	Х					
		1h	$\pm 5 \min$	Х					
Cycle 2	D1	2h	$\pm 10 \min$	Х					X
- , • • • 2		4h	$\pm$ 15 min	Х					
		6h	$\pm 15 \min$						
		8h	$\pm$ 30 min	X					
	D2	24h d	$\pm 1h$	Х					

Table 4: Schedule for PK and Immunogenicity Blood Sampling by Study Drugs in Phase Ib

			BLU-554 a			CS1001	a		
Da	у	Time	Time window	PK Sampling	Time	Time window	PK Sampling	ADA Sampling of CS1001	ECG a, e
					0 (Predose	30 min prior to dosing	Х	Х	Х
	D1	BLU-554 dosing b			CS1001 dosing b				
Cycle 4					EOI+30 min	$\pm 15 \min$	X		Х
					EOI+6h	$\pm$ 30 min	Х		
	D2				EOI+22.5h d	$\pm 1 h$	Х		
	D8				EOI+168 h	± 1 d	Х		
	D15				EOI+336h	± 1 d	Х		
Cycle 5	D1				0 (Predose)	30 min prior to dosing	Х	Х	
C7, C10, C13 and									
C16, and	D1					30 min prior	v	V	
every 8	D1				0 (Predose)		Х	Х	
cycles						to			
afterwards						dosing			

Abbreviations: EOI, end of infusion; ADA, anti-drug antibody; PK, pharmacokinetics

a. It is important that PK sampling occurs as close as possible to the scheduled time. PK and immunogenicity sampling and ECG collection should be performed on the same day. Detailed sequential procedures are: 1) Scheduled triplicate ECG with an interval of at least 5 mins; 2) Vital sign measurements; 3) PK blood sampling; and 4) Any other tests and assessment required by the study.

b. After BLU-554 is administered, the subject should be intravenously infused with CS1001 as soon as possible. For PK blood sampling, the recommended infusion time of CS1001 is 90 minutes.

c. Collect two samples at one time point with BLU-554 blood sample be collected firstly and then CS1001 blood sample.

d. The 24h PK sample of BLU-554 and the EOI+22.5h PK sample of CS1001 must be collected prior to dosing on the same day.

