# Figure 4:Efficacy Measurements for BLU-554 in a Subject-derived Xenograft Tumor Model with FGF19 Up-regulation in the Absence of Genomic Amplification

Mice bearing LIX-066 xenograft tumors were dosed orally with 30, 100, or 200 mg/kg BLU- 554 bid. The LIX-066 xenograft models HCC tumors that are IHC+, FISH-. A significant decrease in tumor growth was observed. Data points represent group mean, and error bars represent standard error of the mean (SEM).

Safety pharmacology studies revealed that BLU-554 inhibits human ether-a-go-go-related gene (hERG) channel activity in vitro with an average IC50 of 6.26  $\mu$ M by single cellular electrophysiological recordings. The pharmacologic specificity of BLU-554 was assessed against a panel of 55 pharmacological targets including receptors, transporters, and enzymes. Compound binding was calculated as percentage inhibition of the binding of a radioactively labeled ligand specific for each target. Assays for the following targets showed >50% inhibition by BLU-554 at 10  $\mu$ M screening concentration: A3 adenosine receptor,  $\alpha$ 2 adrenergic receptor, chloride ion channel,  $\kappa$ -opioid receptor,

CSTONE Confidential Page 40 of 139 melatonin receptor MT1, sodium ion channel site 2, and the nociceptin receptor. The relevance of this binding was not apparent in the dog and mouse 28-day Good Laboratory Practice (GLP) toxicology studies and so the clinical significance of these interactions is unknown.

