# Pharmacokinetics

The single dose (Cycle 1 Day 1 [C1D1]) and steady state (Cycle 1 Day 15 [C1D15]) pharmacokinetics of BLU-554 following QD and BID oral administration have been evaluated in subjects in Study BLU-554-1101. The mean plasma BLU-554 concentration-time profiles for each dose level on C1D1 and C1D15 are shown in **Figure 7** 

Following administration of single oral doses of BLU-554 ranging from 140 to 900 mg, the median time to peak concentration ( $T_{max}$ ) ranged from 1.5 to 2 hours postdose, and the mean (of all dose groups) plasma elimination half-life ( $t_{1/2}$ ) of BLU-554 was 16.5 hours. After a single dose and repeat dosing of BLU-554, systemic exposure increased in a dose-dependent manner. No significant drug accumulation (Rac  $\leq 1.6$ ) was observed after repeat dosing of BLU-554 (dose range: 140 – 900 mg QD; 200 and 300 mg BID), consistent with the observed half-life. The steady state (C1D15) geometric mean (%CV; n) Cmax and AUC0-t of BLU-554 at the RP2D of 600 mg QD was 8733 ng/mL (36.1%; n=72) and 91386 h•ng/mL (41.8%; n=65), respectively.

Figure 7: Mean (+StdDev) Plasma Concentration-Time Profiles of BLU-554 on C1D1 (Single Dose) and C1D15 (Steady State) Following Once Daily or Twice Daily Oral Administration (Study BLU-554-1101)

Abbreviations: BID = twice daily; C1D1 = Cycle 1, Day 1; C1D15 = Cycle 1, Day 15; QD = once daily; StdDev = standard deviation. Data cut-off date: 22 June 2018.

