## 10.3. SAFETY ANALYSIS

Adverse events and toxicities will be evaluated according to NCI-CTCAE v5.0. Safety assessment will be conducted through medical review of adverse events and laboratory values. The incidence of DLT in the DLT population will be evaluated by dose group.

Treatment emergent adverse events (TEAE) will be summarized by preferred term, system organ class, NCI-CTCAE severity grade and causality with investigational product.

TEAE is defined as (regardless of severity)

- Any adverse event following initiation of treatment
- Adverse event that exists at the time of initiation of treatment but begins to worsen following initiation of treatment
- Adverse event that has occurred and remitted prior to treatment but recurs following initiation of treatment

Vital signs (including weight changes) and clinical laboratory values will be descriptively summarized by dose. ECG data will be evaluated and any abnormality will be listed. A tabular listing and summary of subjects in whom treatment with the investigational product is discontinued due to AE will be provided. A listing of death data will be provided.

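### SAP 3.5.6 reports only an overall ECG evaluation and clinically significant abnormalities, so a mean or moderate QTcF shift would not be quantified despite triplicate ECGs timed to BLU-554 dosing

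*SAP*

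**What the plan says.** **Planned analysis.** SAP 3.5.6 states "At each visit, the overall ECG evaluation will be summarized" and "All abnormal and clinically significant 12-lead ECG findings will be tabulated". Protocol 10.3 is wider on listings: "ECG data will be evaluated and any abnormality will be listed". The synopsis, reproduced as SAP Appendix 1, also lists abnormal ECG findings without a clinical-significance filter. Neither document specifies a QTcF summary, a change from baseline, threshold counts, a rule for combining triplicates, or an exposure analysis. SAP 3.7.1 refers pharmacokinetic analysis to a separate PK SAP.

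**Planned collection.** Protocol Table 2, footnote i, says of Cycles 1, 2 and 4: "In case of PK sampling, ECG should be performed for 3 consecutive times with an interval of 5 minutes each time". Footnote a to Tables 4 and 5 puts this first in the order of procedures, before vital signs and the PK draw: "Scheduled triplicate ECG with an interval of at least 5 mins". Both tables place ECGs at predose and 2 h after BLU-554 on Day 1 of Cycles 1 and 2.

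**Background.** Protocol 2.3.1.1 reports that "BLU-554 inhibits human ether-a-go-go-related gene (hERG) channel activity in vitro with an average IC50 of 6.26" µM. Section 2.4.1.1 gives a median Tmax of 1.5 to 2 h. Section 5.3 excludes subjects with QTcF above 480 ms. ECG is named in the Phase Ib primary safety endpoint and the Phase II secondary one.

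**The concern.** The ECG schedule has a clear purpose: three tracings reduce measurement noise, and the 2 h time point falls near peak BLU-554 concentration, after the first dose and again at the start of Cycle 2. The analysis does not use any of this. An overall evaluation carries no interval in milliseconds. A summary per visit need not separate predose from 2 h on the same day. The SAP's baseline is the last valid measurement before treatment, which for a triplicate would be one tracing of three.

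The same SAP gives laboratory data (3.5.5) and vital signs (3.5.9) a change from baseline at each visit. ECG, the assessment linked to a stated in vitro signal, gets no numerical summary.

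At stake is whether the study, having collected suitable ECGs, can say if the combination is accompanied by a QTcF shift and how large it is.

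**Working it through.** The documents give no QTc target, power or precision, so there is no planned figure to reproduce. The check is textual, with three supporting calculations on stated assumptions.

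**1. Collection against analysis**

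| Feature of the data | Where set | Used in SAP 3.5.6? |
|---|---|---|
| Triplicate tracings | Protocol Tables 2 to 5, footnotes | No averaging rule |
| Predose and 2 h, Cycles 1 and 2 | Protocol Tables 4 and 5 | Summary is per visit |
| QTc by Fridericia | Protocol 5.3, eligibility only | Not mentioned |
| All abnormal ECGs | Protocol 10.3 | Only those also clinically significant |

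**2. Precision of a mean QTcF change**

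Half-width of the 90% CI = t(0.95, n−1) × SD / √n. The SD of the change, with triplicates averaged, is assumed to be 10, 15 or 20 ms. Sample sizes are about 40 for Phase II (the SAP summarises Phase II in aggregate), 25 if only the FGF19 IHC+ group is enrolled, and 12 for the whole of Phase Ib.

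Example: n = 40, SD = 10 gives 1.685 × 10 / 6.325 = 2.7 ms.

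| n | SD 10 | SD 15 | SD 20 |
|---|---|---|---|
| 40 | 2.7 ms | 4.0 ms | 5.3 ms |
| 25 | 3.4 ms | 5.1 ms | 6.8 ms |
| 12 | 5.2 ms | 7.8 ms | 10.4 ms |

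A shift of 10 to 20 ms would stand clear of zero in Phase II in every case. With 12 subjects, and still more within a Phase Ib dose group, it might not.

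**3. Chance that such a shift produces a striking individual change**

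Under a normal model at one time point, p = 1 − Φ((60 − shift)/SD). The chance that at least one of 40 subjects has an increase above 60 ms is 1 − (1 − p)^40. Example: shift 15, SD 15 gives z = 3, p = 0.0013 and a chance of about 5%.

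| True mean shift | SD 10 | SD 15 | SD 20 |
|---|---|---|---|
| 10 ms | 0.0% | 2% | 22% |
| 15 ms | 0.0% | 5% | 39% |
| 20 ms | 0.1% | 14% | 60% |

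In most of these settings a real average shift would leave no subject with a change above 60 ms. Several postdose time points per subject would raise these chances somewhat.

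**4. Exposure context only**

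The geometric mean steady-state Cmax at 600 mg QD is 8733 ng/mL (Protocol 2.4.1.1). Molecular weight is not in the documents. At an assumed 400 to 600 g/mol, 8733 / MW is 21.8 to 14.6 µM, and division by 6.26 µM gives 3.5 to 2.3. This compares total plasma concentration with an in vitro IC50. The unbound fraction is not given, so no safety margin follows.

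**The case against.** **Prolongation would not be invisible.** A reader might infer that a QTc effect could pass through every table unseen. The documents do not support that. Protocol 7.1.3 has a qualified physician assess each ECG and requires abnormal ones to be repeated. An abnormal reading would be expected to count in the overall evaluation, although the SAP does not define its categories. QT prolongation reported as an adverse event would enter the TEAE tables by preferred term and CTCAE grade. What remains is narrower: the size of any average or moderate change.

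**An exposure analysis may exist elsewhere.** The PK SAP is not among the documents and could contain a concentration-QTc analysis, so its absence from the overall plan cannot be claimed. A descriptive QTcF table still belongs in the SAP section that covers ECG safety.

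**The pairing with BLU-554 PK is partial.** Cycle 4 ECGs accompany CS1001 samples only; no BLU-554 concentration is drawn then. On Cycle 1 Day 1 the 2 h ECG may be taken 1 to 4 h after dosing, while the PK window is ±10 min. This stands and limits the plot.

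**The in vivo evidence points the other way.** The 28-day dog study found no functional cardiovascular effect on ECG (Protocol 2.3.3.1), and dog exposure at the highest non-severely toxic dose approximates human exposure at 600 mg. QT events are not named among the common related events in 115 treated subjects. A reader might take the Cmax/IC50 ratio as evidence that BLU-554 prolongs QT; it is not.

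**The protocol promises no QTc endpoint.** True. The point is therefore a cheap improvement in analysis, apart from the listing, where the SAP is narrower than the protocol.

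**Conclusion.** The point holds in a limited form. Followed exactly, SAP 3.5.6 would not quantify a mean or moderate QTcF shift within readings judged normal or not clinically significant, and its ECG table is narrower than the listing in Protocol 10.3. Phase II could estimate a mean change to within about 2.7 to 5.3 ms (90% CI half-width, n = 40), or 3.4 to 6.8 ms with 25 subjects. These figures rest on an assumed SD of 10 to 20 ms; the chances of a striking individual change also rest on a normal model.

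The documents do not show that BLU-554 prolongs QT in patients, that marked individual prolongation would be missed, or that no exposure analysis is planned anywhere. The change should be made because the ECGs are already scheduled and the cost is small.

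**What to change.** Amend SAP 3.5.6 as follows.

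1. Average each triplicate, and take the mean of the predose Cycle 1 Day 1 triplicate as the QTcF baseline.
2. Tabulate QTcF and its change from baseline by nominal time point, with predose and 2 h shown separately and a 90% CI for the mean change.
3. Count subjects with QTcF above 450, 480 and 500 ms, and with increases above 30 and 60 ms.
4. List all abnormal ECGs, as Protocol 10.3 states, and flag those judged clinically significant.
5. For Cycles 1 and 2 only, using actual times, plot change in QTcF against BLU-554 concentration, or cite the PK SAP if it already plans this.

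The cost is a few tables and one plot, with no new visits or samples. This assumes that QTcF, or QT and RR, are recorded in the eCRF for each tracing. The documents do not say so, and it should be checked first.
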